12.1.11. Clinical Laboratory Evaluations

The central laboratory will analyze the samples. Further details of the procedures to be followed for sample collection, storage, and shipment will be documented in a laboratory manual.

Repeat testing for protocol required laboratory tests are to be analyzed by the central laboratory. Additional testing may be performed at the discretion of the Investigator and analyzed by the local laboratory. Approval from the Medical Monitor must be obtained if retest is required to be repeated > 2 times.

- Hematology: Red blood cell count, total and differential WBC count (basophils, eosinophils, lymphocytes, monocytes, and neutrophils), platelet count, Hb, hematocrit, mean corpuscular volume, mean corpuscular hemoglobin, and mean corpuscular hemoglobin concentration. Total WBC count and all differential WBC counts will be blinded information for the treating Investigator after initiation of investigational drug. Of note, WBC, basophil, eosinophil, lymphocyte, monocyte, and neutrophil counts will not be disclosed to preserve the blind.

During the treatment period, WBC differential results will be available to an unblinded medical reviewer not directly participating in study conduct. Reductions in ALC levels is a known pharmacodynamic effect of RPC1063. If any of the following results are observed, the Investigator will be notified and asked to repeat the laboratory tests within approximately 7 days:

- Absolute neutrophil count (ANC) < 1000 cells/ μ L
- Absolute lymphocyte count (ALC) < 200 cells/ μ L

If the ANC is confirmed below the 1000 cells/ μ L limit, the Investigator will be requested to closely monitor for risk of serious infection and institute appropriate follow-up, at the discretion of the Investigator.

If the ALC is confirmed below the 200 cells/ μ L limit, the Investigator will temporarily discontinue investigational drug and then consult with the Medical Monitor. Laboratory testing will be repeated weekly during the treatment period until the ALC > 500 cells/ μ L. When ALC has returned to > 500 cells/ μ L, the treatment may be reinitiated at the Investigator's discretion (see [Section 9.1.3](#) for instructions on resuming treatment after missing doses).

For patients who have a confirmed ALC below the 200 cells/ μ L limit and permanently discontinue from participation in the study, central laboratory testing will continue every 14 days (\pm 3 days) after the Early Termination Visit until the ALC is above the lower limit of normal.

- Chemistry:
Full chemistry panel at Screening: sodium, potassium, chloride, calcium, magnesium, phosphate, blood urea nitrogen, glucose, HbA1c, albumin, alkaline phosphatase, creatinine, ALT, AST, gamma glutamyltransferase (GGT), total bilirubin, conjugated bilirubin, total cholesterol, triglycerides, high-density lipoprotein, and low-density lipoprotein, C-reactive protein
 - All other visits: blood urea nitrogen, albumin, alkaline phosphatase, creatinine, ALT, AST, GGT, total bilirubin, conjugated bilirubin, C-reactive protein. Of note, C-reactive protein will not be disclosed to preserve the blind.
- Urinalysis: Leukocytes, specific gravity, bilirubin, blood, glucose, ketones, pH, protein, and urobilinogen
- The central laboratory will analyze routine blood samples. Details regarding collection of samples, shipment of samples, reporting of results, laboratory reference ranges, and alerting abnormal values will be supplied to the site before site initiation in a trial laboratory manual. The results of the analysis will be made available to each site by the central laboratory.
- Investigators will be asked to comment on those abnormalities on the respective laboratory result page, including a notation of the clinical significance of each abnormal finding in the patient's source documents. The laboratory sheets will be filed with the patient's source documents.

- Pregnancy test: Serum β -hCG must be performed at Screening in females of childbearing potential. Urine β -hCG will be performed in females of childbearing potential at each scheduled visit. Between scheduled visits up until the 90-day Safety Follow-up Visit, monthly home urine pregnancy tests should be performed by the patient. If a urine pregnancy test result is positive, the Investigator will instruct the patient to suspend further study dosing, if applicable, and schedule a follow-up appointment as soon as possible. A serum pregnancy test will be performed for confirmation, including after the 90-day Safety Follow-up visit, if needed.
- Serology testing will be performed at Screening to determine the patient's immune status with respect to the following viral infections:

VZV

- A VZV titer will be performed to determine if the patient has immunity (positive IgG result to *Varicella Zoster* virus). If VZV antibody titer is negative, the patient may choose to receive VZV vaccination in order to qualify for the study. If the patient receives a VZV vaccination, randomization can occur at a minimum of 30 days after vaccination has been completed.

HIV

- A HIV antibody test will be performed. Patients testing positive for HIV (ELISA test result, confirmed by Western blot) will be excluded from the trial.

HAV

- An anti-hepatitis A virus (HAV) antibody (anti-HAV IgM) test will be performed. Patients testing positive will be excluded from the trial, unless they are indicative of prior hepatitis A that is considered cured and accompanied by normal liver transaminase values.

HBV

- Anti-hepatitis surface (HBs) antigen and anti-hepatitis B core (HBc) antigen test will be performed
- Patients who test positive for HBs antigen will be excluded from the trial.
- For patients who test positive only for antibody to HBc antigen, an HBV DNA test must be performed.
- If the HBV DNA test is negative (without anti-viral therapy) and the liver function tests (LFTs) are normal, the patient will be eligible for this trial. These patients will undergo periodic monitoring for HBV DNA during the trial.

HCV

- A HCV antibody (anti-HCV IgG or IgM test) will be performed.

- Patients testing positive for HCV antibody and a positive confirmatory test will be excluded from the trial.

12.2. Adverse Events and Serious Adverse Events

12.2.1. Definition of Adverse Events

An AE is any untoward medical occurrence in a patient or clinical investigation patient administered a pharmaceutical product, which does not necessarily have a causal relationship with this treatment. An AE can therefore be any unfavorable and unintended sign (including an abnormal laboratory finding), symptom, or disease temporally associated with the use of a medicinal product, whether or not considered related to the medicinal product (ICH E2A, II.A.1).

Ulcerative colitis disease relapse and related symptoms will be monitored as trial endpoints and thus will not be recorded as AEs, unless it qualifies as a serious AE to trigger safety reporting as described in [Section 12.2.7](#).

In cases of surgical or diagnostic procedures, the condition/illness leading to such a procedure is considered as the AE rather than the procedure itself.

An Adverse Drug Reaction (ADR) is defined as all noxious and unintended responses to a medicinal product related to any dose (ICH E2A, II.A.2).

An Unexpected ADR is defined as an adverse reaction, the nature of which is not consistent with the applicable product information (ICH E2A, II.A.3).

Each AE is to be evaluated for duration, severity, seriousness and causal relationship to the investigational drug. The action taken and the outcome must also be recorded.

12.2.2. Definition of Serious Adverse Events

Definition of Serious Adverse Event (SAE): An SAE (experience) or reaction is any untoward medical occurrence that at any dose (ICH E2A, II.B):

- Results in death
- Is life-threatening

NOTE: The term life-threatening” in the definition of “serious” refers to an event in which the patient was at risk of death at the time of the event; it does not refer to an event which hypothetically might have caused death if it were more severe.

- Requires inpatient hospitalization or prolongation of existing hospitalization
- Results in persistent or significant disability/incapacity, or
- Is a congenital abnormality/birth defect

Medical and scientific judgment should be exercised in deciding whether expedited reporting is appropriate in other situations, such as important medical events that may not be immediately life-threatening or result in death or hospitalization but jeopardize the patient or may require intervention to prevent one of the other outcomes listed in the definition above. *These should also usually be considered serious.*

Examples of such events are intensive treatment in an emergency room or at home for allergic bronchospasm; blood dyscrasias or convulsions that do not result in hospitalization; or development of drug dependency or drug abuse.

In case of a fatality, the cause of death is considered as the SAE, and the death is considered as its OUTCOME.

12.2.3. Assessment of Adverse Event Severity

The severity of the AE will be characterized as “mild, moderate, or severe” according to the following definitions:

- Mild events are usually transient and do not interfere with the patient’s daily activities.
- Moderate events introduce a low level of inconvenience or concern to the patient and may interfere with daily activities.
- Severe events are incapacitating and interrupt the patient’s usual daily activity.

12.2.4. Assessment of Adverse Event Relationship to Investigational Drug

The causal relationship between the investigational drug and the AE has to be characterized as unrelated, unlikely, possible, probable, or related. This medical assessment should be made as soon as feasible when reporting an SAE.

The Investigator is requested to assess the relationship of any AEs to treatment using the following definitions:

Unrelated: Those AEs which are clearly and incontrovertibly due to extraneous causes (concurrent drugs, environment, etc.) and do not meet the criteria for drug relationship listed under Unlikely, Possible, Probable, or Related.

Unlikely: An AE may be considered unlikely if it includes at least the first two features:

- It does not follow a reasonable temporal sequence from administration of the drug
- It could readily have been produced by the patient’s clinical state, environmental or toxic factors, or other modes of therapy administered to the patient
- It does not follow a known pattern to the suspected drug
- It does not reappear or worsen when the drug is re-administered

Possible: an AE may be considered possible if it includes at least the first two features:

- It follows a reasonable temporal sequence from administration of the drug
- It could readily have been produced by the patient’s clinical state, environment or toxic factors, or other modes of therapy administered to the patient
- It follows a known response pattern to the suspected drug

Probable: an AE may be considered probable if it includes at least the first three features:

- It follows a reasonable temporal sequence from administration of the drug

- It could not be reasonably explained by the known characteristics of the patient's clinical state, environmental or toxic factors or other modes of therapy administered to the patient
- It disappears or decreased on cessation or reduction in dose. There are exceptions when an AE does not disappear upon discontinuation of the drug (eg, bone marrow depression, fixed drug eruptions, tardive dyskinesia, etc.)
- It follows a known pattern of response to the suspected drug

Related: an AE may be considered related if it includes all of the following features:

- It follows a reasonable temporal sequence from administration of the drug
- It could not be reasonably explained by the known characteristics of the patient's clinical state, environmental or toxic factors or other modes of therapy administered to the patient
- It disappears or decreased on cessation or reduction in dose. There are exceptions when an AE does not disappear upon discontinuation of the drug (eg, bone marrow depression, fixed drug eruptions, tardive dyskinesia, etc.)
- It follows a known pattern of response to the suspected drug
- It reappears or worsens if the drug is re-administered

All efforts should be made to classify the AE according to the above categories.

After initiation of investigational drug, all AEs, regardless of relationship to investigational drug, will be recorded until the patient completes his or her last trial visit.

12.2.5. Reporting of Serious Adverse Events

Reporting requirements for SAEs will be managed on behalf of the Sponsor by the CRO. Full details of the procedures to be adopted will be documented in a safety management plan approved by responsible parties, in brief:

The Investigator will report any SAE that occurs to any patient from the time written informed consent/assent is signed through the last visit. All SAEs that occur within 90 days of the last dose of treatment with the investigational drug, whether or not considered related to the investigational drug, must also be reported. Any SAE that is ongoing when the patient completes the trial or discontinues from the trial will be followed by the Investigator until the event has resolved, stabilized, or returned to Baseline status.

Any AE considered serious by the Investigator or Sub-investigator or that meets serious criteria should be reported to the CRO's Pharmacovigilance group using the designated SAE reporting forms and procedures. Data entry must be completed within 24 hours from the time the trial site personnel first learned of the event.

[REDACTED]

[REDACTED]

The initial report should be promptly followed by detailed, written reports, which will include copies of hospital case records, discharge summaries, autopsy reports, and other documents when requested and applicable. For unrelated cases, a full detailed case description may negate the need for additional hospital case records, discharge summaries, etc.

12.2.5.1. Reporting of Serious Adverse Events to Regulatory Authorities and Investigators

Investigators will be notified by the CRO of all SAEs that require prompt submission to their IRB or IEC. Investigators should provide written documentation of IRB/IEC notification for each report to the CRO. The CRO will ensure that all SAEs are reported to the appropriate regulatory authorities as required. Reporting of SAEs must comply with ICH E6, 4.11.1.

12.2.6. Adverse Events of Special Interest

Potential AEs that may be a consequence of S1P₁ modulation will be closely monitored during the trial. These AEs include bradycardia, heart conduction abnormalities (2nd degree and higher AV block), macular edema, malignancy, serious or opportunistic infection, pulmonary effects, and hepatic effects. An independent DSMB for the trial will perform quarterly safety reviews starting after the first patient is dosed.

Special considerations regarding monitoring for these events are as follows:

- Bradycardia and heart conduction abnormalities (eg, symptomatic bradycardia, 2nd degree AV block, QT prolongation):
 - Patients will be closely monitored in the clinic after their first dose of the initial dose escalation regimen for a period of 6 hours after treatment. Electrocardiograms will occur predose and at Hour 6 following dosing, with more frequent assessments if clinically indicated. Resting pulse and blood pressure in the sitting position will be assessed predose and then hourly for 6 hours following dosing. See the monitoring guidelines in [Section 12.1.10](#) for further details.
 - Investigators should be particularly cautious with patients who have a pulse rate < 55 bpm prior to administration of the investigational drug. Atropine IV is recommended as the first line treatment of bradycardia, up to a maximum daily dose of 3 mg. In general, the common guidelines for treatment of bradycardia (eg, Advanced Cardiac Life Support guidelines) should be followed as appropriate.
- Pulmonary effects
 - Any condition that might affect the outcome of pulmonary function testing including infection, respiratory symptoms, occupational exposures (including asbestos) and cigarette smoking needs to be collected before PFT testing and transcribed to the pulmonary function tests eCRF page. If patients have decline in PFT values (FEV1 and/or FVC) below 50% of the predicted values, treatment

should be discontinued. If a patient discontinues due to respiratory AE, the Investigator should ensure that the patient has adequate evaluations as clinically indicated by a pulmonologist (consider PFTs, chest X-ray or high resolution computed tomography, based on findings of the other exams) at the time of the AE. For patients with pulmonary nodules, lung biopsy should be considered (Cryptococcus pneumonia and pulmonary TB have been reported with fingolimod). Further evaluations will be conducted until such time as resolution is confirmed or no further improvement is expected by the Investigator (based on a follow-up period of not less than 3 months).

- Hepatic effects
 - If patients have elevations in the LFTs (ALT or/and AST) ≥ 3 times the ULN, a retest should be performed as soon as possible but not later than 14 days after the original test. Upon confirmation of the abnormality, retests should be performed weekly until the elevated LFT decreases to below 3 times the ULN. At any time, if any of the following occur and there are no apparent alternative causes for the finding, the investigational drug must be permanently discontinued:
 - ALT or AST $> 8x$ ULN or
 - ALT or AST $> 5x$ ULN with confirmation, within 2 weeks or
 - ALT or AST $> 3x$ ULN and (total bilirubin $> 2x$ ULN) or
 - ALT or AST $> 3x$ ULN with the appearance of fatigue, nausea, vomiting, right upper quadrant pain or tenderness, fever, rash, and/or eosinophilia ($> 5\%$).

The Investigator should establish causality

After discontinuation due to elevation of ALT or AST $> 5x$ ULN or concurrent elevations of ALT or AST $> 3x$ ULN and bilirubin $> 2x$ ULN, further liver function evaluation should be performed (for example, coagulation panel and alkaline phosphatase) in consultation with the Medical Monitor.

- Macular edema
 - For patients with abnormal OCT findings or with visual signs or symptoms of new onset macular edema that develop following initiation of treatment, a general ophthalmologic examination including eye history, visual acuity, and dilated ophthalmoscopy will also be performed
 - Investigational drug must be discontinued in any patient who has a confirmed diagnosis of macular edema that is of new onset since Baseline
 - Patients with a diagnosis of macular edema must be followed up monthly and more frequently if needed based on the ophthalmologist's judgment

- Malignancies
 - Because RPC1063 is an immunomodulator, patients should be carefully monitored for malignancies (including dermatologic malignancy)
 - The Investigator will complete a dermatological examination for monitoring of the potential development of new cutaneous malignancies during the trial. Patients with any suspicious finding noted during the examination will be referred to an appropriately qualified dermatologist for evaluation and treatment, if warranted
- Serious or opportunistic infections
 - TB, serious bacterial infections, systemic fungal infections, viral infections such as herpes infections (including herpes zoster and disseminated herpes simplex) and protozoan infections will be considered AEs of special interest

12.2.7. Monitoring of Patients with Adverse Events, Serious Adverse Events, and Adverse Events of Special Interest

Investigators must carefully monitor each patient for AEs. This includes clinical laboratory variables. The reporting of AEs will begin at Induction Day 1 post first dose for all randomized patients. The reporting of SAEs for any patient will begin from the time written informed consent/assent is signed through the last visit, as detailed in [Section 12.2.5](#). Assessments must be made of the seriousness, severity, and relationship to the administration of the investigational drug. After the initial AE/SAE report, the Investigator is required to follow up proactively each patient and provide further information to the CRO on the patient's condition. During the trial, all AEs/SAEs should be followed up to resolution unless the event is considered by the Investigator to be unlikely to resolve due to the patient's underlying disease, or the patient is lost to follow-up. Safety reporting must comply with ICH E6, 4.11.

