Ozanimod causes a dose-dependent reduction in peripheral lymphocyte count because of reversible retention of lymphocytes in lymphoid tissues. In the controlled RMS trials, mean absolute lymphocyte counts during treatment with ozanimod were approximately 45% of baseline values. Ozanimod may therefore increase the susceptibility to infections. In the Phase 3 RMS program, 0.4% of subjects on 0.46 mg ozanimod and 3.3% of subjects on 0.92 mg ozanimod developed ALC below $0.2 \times 10^9/L$ with no distinct pattern of timing. An association between ALC $< 0.2 \times 10^9/L$ and serious or opportunistic infections was not detected; however, an increased risk of infection cannot be ruled out.

In active-controlled completed RMS clinical trials, the overall rate of infections (35%) with Ozanimod was similar to that of IFN β -1a. Ozanimod treatment was associated with a higher frequency of viral upper respiratory tract infections, urinary tract infections, and herpes zoster. The overall rate of serious infections was similar between ozanimod (1%) and IFN β -1a (0.8%) in active-controlled MS clinical trials (also refer to protocol [Section 6.2.5](#)).

Phase 2 UC and CD data follow a similar pattern.

After discontinuing ozanimod 0.92 mg, the median time to recovery of peripheral blood lymphocytes to the normal range was 30 days, with approximately 90% of subjects recovering within 90 days.

Vaccinations

No clinical data are available on the efficacy and safety of vaccinations, including live attenuated, in subjects taking ozanimod. The use of live attenuated vaccines is to be avoided during treatment with ozanimod and for 90 days after treatment discontinuation.

Pulmonary Effects:

Pulmonary function is known to be affected by fingolimod, a non-selective S1P receptor modulator, and increased collagen or fibrin deposition in the lung as has been reported in toxicology studies with fingolimod. In nonclinical studies, ozanimod did not induce smooth muscle hypertrophy, and no effect on respiratory function was observed with ozanimod administration in rodents. In patients with multiple sclerosis, the pulmonary data indicate that mild reductions in FEV1 and DLCO occurred early in treatment with ozanimod 1 mg but were not clinically meaningful and did not progress. Pulmonary effects are not considered to be a risk associated with ozanimod treatment.

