6.7. Result Blinding

Before unblinding Cohort 1 treatment codes, results of PK, total and differential white blood cell (WBC) count (basophils, eosinophils, lymphocytes, monocytes, and neutrophils), fecal calprotectin, and C-reactive protein beyond first dose will not be disclosed to preserve the blind.

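### The liver stopping rule counts eosinophilia as a qualifying feature, but eosinophil results are withheld from the investigator and the plan states no route by which this one reaches them

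*Protocol*

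**What the plan says.** **Protocol Section 12.2.6 (hepatic effects)** lists four liver findings. If any one occurs without another evident cause, "the investigational drug must be permanently discontinued". The fourth is ALT or AST above 3x ULN "with the appearance of fatigue, nausea, vomiting, right upper quadrant pain or tenderness, fever, rash, and/or eosinophilia", with eosinophilia given as above 5%. The section then says "The Investigator should establish causality" and gives no other role the task of checking the eosinophil element.

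**Protocol Section 12.1.11 (hematology)** says "Total WBC count and all differential WBC counts will be blinded information for the treating Investigator after initiation of investigational drug", and then "Of note, WBC, basophil, eosinophil, lymphocyte, monocyte, and neutrophil counts will not be disclosed to preserve the blind". An unblinded medical reviewer outside study conduct can see the differential. Two results lead to notice to the investigator: ANC below 1000 cells/µL and ALC below 200 cells/µL. Repeats of protocol-required tests go to the central laboratory. Further tests may be run locally if the investigator chooses.

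**SAP Section 6.7** applies the same blinding for the Induction Period: "Before unblinding Cohort 1 treatment codes, results of PK, total and differential white blood cell (WBC) count", with eosinophils among the cell types listed, are not disclosed beyond the first dose.

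**The concern.** A mandatory stopping rule needs each of its inputs to reach whoever applies it. Here the investigator applies the rule, and one input that is sufficient in combination with raised ALT or AST is deliberately hidden from the investigator. The protocol already has a relay for hidden white cell results that call for action, but this result is not on its list.

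At stake is the treatment of a patient who meets the sponsor's own criterion. Appendix 3 names liver injury as an important potential risk and relies on the protocol's discontinuation rules to deal with enzyme elevations. A site that noticed the gap could close it with a local differential, but for a blinded patient that would put the lymphocyte count in front of the investigator.

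**Working it through.** No plan figure is in question, so the check is a cross-reading of the sections.

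**Which inputs of the hepatic rule can the investigator see?**

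| Input in Section 12.2.6 | Available to the investigator? | Basis in Section 12.1.11 |
|---|---|---|
| ALT, AST | Yes | Chemistry; only C-reactive protein is withheld |
| Total bilirubin | Yes | Same |
| Symptoms, fever, rash | Yes | Clinical findings, not blinded |
| Eosinophils above 5% | No | Differential withheld, eosinophils named |

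**Follow one patient through the text.** Take ALT above 3x but not above 5x ULN, bilirubin not above 2x ULN, no listed symptom, eosinophils above 5%, and no other evident cause.

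1. The other three findings in Section 12.2.6 are not met: ALT/AST above 8x, confirmed above 5x, or above 3x with bilirubin above 2x.
2. The fourth is met, through eosinophilia alone. The joining words in "right upper quadrant pain or tenderness, fever, rash, and/or eosinophilia" make one feature sufficient.
3. The investigator sees the ALT, retests within 14 days and then weekly, and finds no qualifying feature.
4. The reviewer can see the eosinophil result. Neither notification trigger is an eosinophil value, and neither is tied to ALT or AST, so no notice follows.
5. The drug continues although the criterion is met.

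**Other routes in the documents.**

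- Local testing is permitted, but Section 12.2.6 does not call for it and Section 12.1.11 does not link it to liver findings.
- The DSMB (Section 12.2.10) reviews aggregate data about four times a year, which does not serve individual stopping decisions.
- Section 12.1.11 says in general that central results go to sites, but the specific non-disclosure of these counts governs.

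**Does the information exist?** Yes. Table 1 schedules hematology and chemistry at the same visits, so the differential from a scheduled visit is already with the reviewer. The text does not say whether hematology is also drawn at the weekly liver retests.

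**The case against.** The strongest reply is that the gap is a missing prompt. Local tests are allowed, so the element can be checked. In open-label Cohort 2 (about 300 of 900 adults) a local differential during induction has no allocation to reveal. SAP Section 11.2 refers to a safety management plan under which events of special interest are adjudicated, and that plan is not among the documents. The rule is also conditional on there being no other evident cause.

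Most of this stands, and it limits the claim. It does not remove the conflict. Nothing readable prompts the local test, Section 12.1.11 makes no exception for Cohort 2, and the notification list omits eosinophils.

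Five stronger readings are tempting and are not supported:

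- **The element can never be applied, and nobody is told.** Local testing is open to the investigator, and an unseen plan may contain a relay.
- **About 22 patients are affected.** Appendix 3 gives ALT of 3x ULN or more in 5.5% of ozanimod patients in MS trials, and 0.055 × 400 = 22 Cohort 1 active patients. The same paragraph puts the median time to elevation at 6 months, against 10 weeks of induction. If that timing carried over, fewer than half (22 / 2 = 11) would arise by Week 10. The figure also counts patients who would need the check, not those with eosinophilia as sole feature.
- **Efficacy is biased through the Physician's Global Assessment.** The primary endpoint and clinical response use the three-component Mayo definition, which excludes that assessment, and endoscopy is read centrally. The other key secondary endpoints do not use it either.
- **Hepatic discontinuations are under-counted.** This is an inference; the documents give nothing to measure it.
- **The 5% threshold is distorted by the drug.** In MS trials "mean absolute lymphocyte counts during treatment with ozanimod were approximately 45% of baseline values". If lymphocytes made up a share L of white cells and other lines were unchanged, the eosinophil percentage would be multiplied by 1/(1 − 0.55L): 1.12 at L = 0.20 and 1.28 at L = 0.40. That range of L is assumed, and the argument concerns the clinical threshold, which is a separate matter. Its one use here is as a caution that a notice about eosinophils might carry a little information about treatment.

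**Conclusion.** The conflict between Protocol Sections 12.2.6 and 12.1.11 is real, and SAP Section 6.7 repeats the blinding side of it. Followed as written, a patient with ALT or AST above 3x ULN whose only accompanying feature is eosinophilia would not be identified from central results. Every other part of the hepatic rule works.

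The number of such patients cannot be estimated from the documents and is probably small. No effect on the primary or key secondary endpoints is shown. The case for repair is that a mandatory safety criterion should work through the protocol's own flow of results, and the repair is cheap. The conclusion assumes that no redacted text or separate plan already supplies the missing route. If one does, the point reduces to a missing cross-reference.

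**What to change.** Reconcile Section 12.2.6 with Section 12.1.11 by stating, for patients with ALT or AST above 3x ULN, who checks the eosinophil element, on which sample, and how the outcome reaches the person who must act. One workable route is the existing unblinded medical reviewer, with the notice worded so that it does not give the count. If the safety management plan already covers this, a cross-reference is enough. Whether the criterion stays as it is, or is changed, is for the sponsor.

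The cost is about one sentence in Section 12.1.11 and one line in the reviewer's instructions. For scheduled visits no new sample, visit or staff is needed. The downside is a few extra notifications to sites, with a small potential to hint at treatment.
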